9.3.4 Exploratory endpoint(s)/estimand(s) analysis

Not applicable.

9.3.5 Other safety analyses

Safety laboratory assessments

Safety laboratory assessments (biochemistry, haematology, glucose metabolism, coagulation parameters (NS), and lipids) will be summarised by time of assessment for each indication, SGA, TS, NS or ISS. All abnormal values will be listed.

Vital signs

Vital signs (electrocardiogram, transthoracic electrocardiogram (TS, NS)) will be summarised by time of assessment for each indication, SGA, TS, NS or ISS. The investigator's evaluation of vital signs will be tabulated by time of assessment for each indication, SGA, TS, NS or ISS.

Antibodies

For confirmed anti-somapacitan antibody positive samples, the anti-somapacitan positive cross-reactivity to hGH antibodies and in vitro neutralising effect will be tabulated by time of assessment for each indication, SGA, TS, NS or ISS.

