2.2.3 Included populations

The current protocol includes four indications associated with short stature and indicated for pharmacological treatment with GH.

Throughout the protocol the following abbreviations and definitions are used for the indications:

- SGA: Small for Gestational Age: Children born small for gestational age with insufficient catch-up growth by 2 years of age or older
- TS: Turner Syndrome
- NS: Noonan Syndrome
- ISS: Idiopathic Short Stature

2.2.3.1 **Small for Gestational Age: Children born small for gestational age with insufficient catch-up growth by 2 years of age or older**

SGA is a heterogenous condition which is a result of impaired foetal growth due to environmental as well as genetic factors, not yet clearly identified. SGA refers to the size of an infant at birth and is defined as a birth length and/or birth weight of at least 2 Standard Deviation Scores (SDS) below the mean for gestational age and sex.¹⁵ The prevalence of SGA has been reported to be between 3.1% and 15.3% depending on the geographical area investigated.¹⁶⁻¹⁹ The variation might be influenced by regional differences in diagnostic practice. Most children born SGA have sufficient GH secretion and IGF-I levels and show spontaneous catch-up growth to a normal height and weight above 2 SDS by 2 years of age. However, approximately 10% of the children do not catch up despite sufficient GH and IGF-I levels and therefore have a markedly reduced final adult height compared to predicted height.^{20, 21}

2.2.3.2 **Turner Syndrome**

TS is a chromosomal disorder occurring in approximately 50 per 100,000 live born girls.^{22, 23} Monosomy X is present in about half of the cases. The remaining cases present a structural X-chromosome aberration or a mosaic karyotype, consisting of a 45X cell line in combination with at least one of the following: 46XX, isochromosome, ring chromosome or marker X, 47XXX, or a whole or partial Y-chromosome. Phenotypic features vary widely in Turner syndrome. Cardinal features include short stature and gonadal failure. Congenital and acquired cardiovascular disease, diabetes, hypothyroidism, impaired hearing, scoliosis, renal abnormalities and neurocognitive disorders are frequently associated diseases.²⁴ Patients with deletions of the distal segment of the short arm of X chromosome (Xp-) including haploinsufficiency of the SHOX (short stature homeobox) have, more often, short stature, skeletal abnormalities, and hearing impairments.²⁵

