2.2.3.3 **Noonan Syndrome**

NS is a relatively common, with widely quoted prevalence of 1 in 1,000–2,500 live births,²⁶ clinically variable and genetically heterogeneous developmental disorder characterized by postnatally reduced growth, distinctive facial dysmorphism, congenital heart defects or hypertrophic cardiomyopathy and variable cognitive deficits. Other associated features include ectodermal and skeletal defects, cryptorchidism, lymphatic dysplasias, bleeding tendency, and, rarely, predisposition to hematologic malignancies during childhood.^{27, 28} NS is regarded as a disorder of upregulated RAS-MAPK signalling.²⁹ NS is nearly always an autosomal-dominant condition, although recently there have been reports of autosomal recessive forms.³⁰ Two-thirds of patients are the first affected person in their family due to a de novo pathogenic variant.³¹ Despite advances in molecular testing of NS an underlying genetic mutation is not identified in 20%–30% of patients. Short stature affects 50–70% of patients with NS.²⁸ At birth the height and weight of the patient are

within the reference range but growth retardation involving height, weight and bone development shows during childhood. The height and weight are usually below -2 SDS for the population.³²

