 - Standing height measured minimum 6 and maximum 18 months prior to screening must be provided. If more than one height measurement has been performed during this period, the most recent measurement should be used. Standing height should be reported in centimetres with one decimal to the nearest 1 mm or in inches with one decimal.
- Parental height: Standing height for both biological parents in centimetres with one decimal to the nearest 1 mm or in inches with one decimal.
- GH status, if available
 - Type of GH stimulation test and result of peak GH values.

Information related to children with ISS

- Height data
 - Standing height measured minimum 6 and maximum 18 months prior to screening must be provided. If more than one height measurement has been performed during this period, the most recent measurement should be used. Standing height should be reported in centimetres with one decimal to the nearest 1 mm or in inches with one decimal.
- Parental height: Standing height for both biological parents in centimetres with one decimal to the nearest 1 mm or in inches with one decimal.
- GH status
 - Type of GH stimulation test and result of peak GH values.

Table 8-2 Diagnostic criteria for Noonan syndrome* (van der Burgt score list)

Feature	A = major	B = minor
1 Facial	
• Typical face	
• Suggestive face
2 Cardiac	
• Pulmonary valve stenosis and/or typical ECG^b	
• Other defect
3 Height	
• <3rd centile (-1.88 SDS)	
• <10th centile (-1.28 SDS)

Feature	A = major	B = minor
4 Chest wall	
Pectus carinatus/excavatum	
Broad thorax
5 Family history	
First degree relative definite Noonan syndrome	
First degree relative suggest Noonan syndrome
6 Other	
All 3 (males): mental retardation, cryptorchidism, lymphatic dysplasia	
One of mental retardation, cryptorchidism, lymphatic dysplasia

Notes:

*Definite Noonan syndrome: 1A plus one of 2A-6A or two of 2B-6B; 1B plus two of 2A-6A or three of 2B-6B.

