8.2.3 Electrocardiograms

12-lead ECG will be obtained according to local practice.

The investigator or a qualified specialist will evaluate the ECG recordings and classify them as either: “normal”, “abnormal, not clinically significant” or “abnormal, clinically significant”.

If the ECG is evaluated as “abnormal, clinically significant” at screening, and judged by the investigator not to be relevant for exclusion from the study, the finding will be recorded as a concomitant illness.

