8.2.4 Transthoracic echocardiogram

A transthoracic echocardiogram (TTE) will be performed for participants with TS or NS.

Any TTE performed within a month prior to screening can be used as baseline data, if the TTE is performed according to the required standards and all relevant parameters are available.

The investigator or a qualified specialist will evaluate the findings from the TTE examination and classify them as either: “normal”, “abnormal, not clinically significant” or “abnormal, clinically significant”. The evaluation and classification will be based on both morphologic and dynamic parameters, as per local practice. Common morphologic parameters are: Left ventricular internal diameter at the end of diastole (LVIDed), Left ventricular internal diameter at the end of systole (LVIDes), End-diastolic interventricular septal thickness (IVSed), End-diastolic left ventricular posterior wall thickness (LVPWed), Left ventricular outflow tract (LVOT) diameter, or right ventricular internal diameter at the end of diastole (RVIDed), whereas dynamic parameters commonly address cardiac output, ejection fraction, and diastolic function.

For the participants with NS, the parameters of interest outlined in [Table 8-3](#) will be recorded in the eCRF.

Table 8-3 Echocardiographic measures to be collected for children with NS

Echocardiographic measures to be collected (NS)	Unit
End-diastolic interventricular septal thickness (IVSed)	mm
End-diastolic left ventricular posterior wall thickness (LVPWed)	mm
Left ventricular internal diameter at the end of diastole (LVIDed)	mm
Left ventricular internal diameter at the end of systole (LVIDes)	mm
Left ventricular mass	g
Left ventricular outflow tract (LVOT) peak gradient	mmHG

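### The only stated display of the ECG and echocardiogram classification is a count per visit, which does not show how many children moved to a worse category, chiefly to a non-significant abnormality

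*Protocol*

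**What the plan says.** Protocol 8.2.3 covers the ECG: "The investigator or a qualified specialist will evaluate the ECG recordings and classify them as either" normal, abnormal but not clinically significant, or abnormal and clinically significant. Protocol 8.2.4 applies the same scale to the TTE in Turner syndrome (TS) and Noonan syndrome (NS): "The investigator or a qualified specialist will evaluate the findings from the TTE examination and classify them as either" one of those three.

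Protocol 9.3.5 gives the reporting rule: "Vital signs (electrocardiogram, transthoracic electrocardiogram (TS, NS)) will be summarised by time of assessment for each indication, SGA, TS, NS or ISS". The second test named there is evidently the echocardiogram. The investigator's "evaluation of vital signs will be tabulated by time of assessment for each indication, SGA, TS, NS or ISS". SAP 4.5 has the same rule. SAP 4.5.3 (additional safety assessments) is marked not applicable, and SAP 4.8 records no change to the protocol analysis. The same protocol section promises a listing of abnormal laboratory values. It promises none for ECG or TTE.

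On the state of children at entry, protocol 2.2.3 says of TS: "Congenital and acquired cardiovascular disease, diabetes, hypothyroidism, impaired hearing, scoliosis, renal abnormalities and neurocognitive disorders are frequently associated diseases". It describes NS by, among other features, "congenital heart defects or hypertrophic cardiomyopathy and variable cognitive deficits". Table 8-2 counts "Pulmonary valve stenosis and/or typical ECG" as a major diagnostic feature of NS. If a screening ECG is abnormal and clinically significant but the investigator does not consider it grounds for exclusion, "the finding will be recorded as a concomitant illness".

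**The concern.** TS and NS carry extra cardiac monitoring, and the trial has no control group, so each child's own baseline is the only reference within the study. A per-visit count gives prevalence at that visit. If some children enter with an abnormal reading, the count mixes old and new abnormalities, and a new one in one child can be offset by a normal re-reading in another. The children counted also change over time. Protocol 7.1 has children who stop treatment at or after visit 7 leave the study, requires treatment to stop at near adult height, and waives the ECG and TTE at the discontinuation visit if they were done in the previous 6 months. What is at stake is whether the report can say how many children worsened from their own starting category.

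**Working it through.** The documents give no expected rate of abnormal ECG or TTE, so there is no figure to reproduce. The check is what two visit counts say about movement within children.

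**Inputs.** n = 10 children, the planned completers per indication (protocol 9.5). The number abnormal at baseline, a, and at a later visit, b, are assumptions.

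**Two categories, everyone assessed twice.** Let x be the newly abnormal and r those who revert to normal. Then b = a − r + x, so x = (b − a) + r. The table supplies b − a but not r. Its limits are max(0, b − a) ≤ x ≤ min(b, n − a).

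| a | b | lowest x | highest x |
|---|---|---|---|
| 0 | 2 | max(0, 2) = 2 | min(2, 10) = 2 |
| 4 | 4 | max(0, 0) = 0 | min(4, 6) = 4 |
| 5 | 5 | max(0, 0) = 0 | min(5, 5) = 5 |
| 6 | 6 | max(0, 0) = 0 | min(6, 4) = 4 |
| 4 | 5 | max(0, 1) = 1 | min(5, 6) = 5 |
| 4 | 3 | max(0, −1) = 0 | min(3, 6) = 3 |

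There are 11 × 11 = 121 possible pairs (a, b). In the 9 × 9 = 81 pairs where some but not all children are abnormal at both visits, x is a range. In the other 121 − 81 = 40 it is fixed. If nobody is abnormal at baseline, the count is exact, so the gap depends on abnormality at entry.

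**Three categories.** With 5 normal, 3 non-significant and 2 significant at both visits, enumerating every 3 × 3 table with those margins gives 0 to 5 children who worsened.

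**Departures.** If d children abnormal at baseline are not assessed later, x among those who remain is (b − a) + r + d. Take 10 children with 4 abnormal, then 8 assessed with 4 abnormal, and no reversions: x = 0 + 0 + d, with d from 0 to 2. Two departures alone leave a range of 0 to 2.

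**What other parts of the plan cover.**
- *Any move to clinically significant, ECG or TTE.* Protocol 10.3.1 makes a clinically significant abnormal safety assessment an adverse event, and 9.3.2 summarises those by preferred term with the number of participants.
- *ECG, normal to non-significant.* No per-child display in any indication.
- *TTE class, normal to non-significant.* No per-child display of the class. Protocol Table 9-2 and SAP 6.1 derive change from baseline to week 26 in four echo SDS values (IVSed, LVPWed, LVIDed, LVIDes), written for TS. Protocol 8.2.4 and Table 8-3 call for recording six echo measures in the eCRF, for NS. As written, the analysis and the recording name different indications.

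**Data set.** Protocol 9.2 and SAP 3 assign all other safety data to the on-treatment set, which runs from first dose to visit 7 at the latest. Read literally, that leaves out the screening ECG and TTE, the permitted TTE from up to a month before screening, and every assessment after visit 7.

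**The case against.** The case against is substantial. First, the transitions that matter most reach the adverse event tables, which carry the primary endpoint. What is left has been judged not clinically significant by the investigator or a specialist. Second, within-child echo change is planned. Third, the ambiguity with complete data is exactly r. If entry abnormalities are lasting syndromic features, few children revert, and the visit counts nearly give the new cases. The 5-and-5 example needs all five abnormal children to become normal while all five normal children become abnormal. Fourth, tabulating by visit does not forbid a baseline comparison. Fifth, the trial is descriptive, with no hypotheses and about 10 completers per indication, and an external data monitoring committee reviews accumulating data.

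The first three limit the size of the point and are accepted. They do not remove it: the non-significant ECG shift has no other route, the echo analysis does not cover the TTE class and its indication is unclear, and departures add ambiguity even when nobody reverts. On the fourth, the plan does not commit to a comparison, and the listing promised for laboratory values but not for ECG or TTE makes it unsafe to assume one. The fifth bears on priority.

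A reader might infer that cardiac worsening could go unseen, or that up to half the children could deteriorate behind a flat table. The documents do not support either: clinically significant worsening is reportable as an adverse event, and no baseline rate or reversion rate is given.

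**Conclusion.** The point holds in a limited form. The planned per-visit counts cannot give the number of children who moved to a worse ECG or TTE category when some are abnormal at entry. The uncovered part is mainly movement to abnormal, not clinically significant: for the ECG in all four indications and for the TTE classification in TS and NS. With complete data its size equals the number of reversions. The range of 0 to 5 in 10 is the mathematical extreme.

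This rests on two assumptions. One is that some but not all children in an indication are abnormal at entry. The protocol's background suggests this for TS and NS in words only, and the TS exclusion of NYHA class II or above, or of heart medication, lowers it somewhat; no matching NS criterion is listed. The other is that the table follows the sentence as written. The paired data will exist, so nothing is lost for good, and neither the primary endpoint nor any hypothesis is affected. It is worth doing because it costs almost nothing.

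**What to change.** In protocol 9.3.5 and SAP 4.5:

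- Keep the per-visit table, which shows prevalence. Add, by indication and separately for ECG and TTE, a shift table of baseline category against the category at each post-baseline visit and against the worst post-baseline category, with a missing category.
- Add a listing of children whose category worsened.
- Define baseline as the last assessment before first dose: the screening ECG or TTE, or the earlier TTE that 8.2.4 permits.
- State that these displays include assessments after visit 7. Without this and the baseline rule, the on-treatment set would exclude both ends of the comparison.
- Reconcile the echo SDS change analysis written for TS (protocol Table 9-2, SAP 6.1) with the echo measures recorded for NS (protocol 8.2.4), and say which indications it covers.
- Correct the name of the echocardiogram in the reporting rule.

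The cost is one added table shell and one listing, a few sentences on baseline and period, and the reconciliation. It needs no new assessment and no change in how children are managed.

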9.3.6 Other analyses

Other parameters

Table 9-2 Overview of other parameters

Title	Time frame	Unit	Details
Child treatment burden measure: GH-INJ-CTB-Physical ^e	Visit 5	Score ^a	GH-INJ-CTB-Physical score at week 13 (visit 5). GH-INJ-CTB – Physical score is derived as the sum of the 4 items (0=Not at all, 1=A little, 2=Some, 3=A lot, 4=Extreme) normalised to a 0-100-point scale as: Physical (question 1-4): (Sum/16)*100
Child treatment burden measure: GH-INJ-CTB-Emotional Well-being ^e	Visit 5	Score ^a	GH-INJ-CTB-Emotional Well-being score at week 13 (visit 5). GH-INJ-CTB – Emotional Well-being score is derived as the sum of the 4 items (0=Not at all, 1=A little, 2=Some, 3=A lot, 4=Extreme) normalised to a 0-100-point scale as: Emotional Well-being (question 5-10): (Sum/24)*100
Child treatment burden measure: GH-INJ-CTB-Interference ^e	Visit 5	Score ^a	GH-INJ-CTB-Interference score at week 13 (visit 5). GH-INJ-CTB – Interference score is derived as the sum of the 4 items (0=Not at all, 1=A little, 2=Some, 3=A lot, 4=Extreme) normalised to a 0-100-point scale as: Interference: (question 11-14): (Sum/16)*100
Child treatment burden measure:	Visit 5	Score ^a	GH-INJ-CTB-Overall treatment burden score at week 13 (visit 5).

Title	Time frame	Unit	Details
GH-INJ-CTB Overall treatment burden ^e			GH-INJ-CTB – Overall treatment burden score is derived as the mean of the GH-INJ-CTB – Physical score, GH-INJ-CTB - Emotional Well-being score and GH-INJ-CTB – Interference score.
Patient Preference: GH-PPQ-Child ^e	Visit 5	Categorical response	Patient Preference GH-PPQ-Child at week 13 (visit 5) (Previous treatment, Current treatment, No preference).
Near adult height (NAH)	18 months prior to screening to end of treatment	Yes/No	Near adult height (NAH) will be derived. NAH is defined as HV < 2 cm/year calculated over a period of at least 9 months, males have reached a bone age of ≥ 16 years and females has reached a bone age of ≥ 14 years. If bone age is not available, then males have reached a chronological age of ≥ 17 years and females have reached a chronological age of ≥ 15 years. Historical height measurements collected at screening will be included in the derivation.
Change in height SDS at the visit when NAH is reached	From baseline (week 0) to the visit NAH is reached	Score ^b	Derived as the Height SDS value at baseline week 0 subtracted from the Height SDS value at the visit where NAH is reached.
Midparental target height (MPH)	Screening (visit 1)	cm	Derived as: Girls TH: (mother's height + father's height-13)/2 ⁵⁶ Boys TH: (mother's height + 13 + father's height)/2 ⁵⁶
MPH SDS	Screening (visit 1)	Score ^c	MPH SDS is derived as: $MPH\ SDS = \frac{Fathers\ height\ SDS + mothers\ height\ SDS}{2}$ Where parental height SDS is derived as: $MPH\ SDS = \frac{Height - population\ mean}{population\ SD}$ The population mean and standard deviation comes from reference data. ⁵⁷
Index of genetic height potential	From baseline (week 0) to the visit NAH is reached	Score ^d	Derived as NAH SDS – MPH SDS

Title	Time frame	Unit	Details
Change in interventricular Septum end diastole (IVSed) SDS	From baseline (week 0) to visit 7 (week 26).	Score ^b	
Derived as the IVSed SDS value at baseline week 0 subtracted from IVSed SDS value at week 26 (visit 7) for Turner syndrome.
 
IVSed SDS is derived as:
 $\text{IVSed SDS}_i = \frac{\ln(\text{IVSed})_i - \text{intercept} + \ln(\text{Weight}_i * \text{slope})}{\text{SD residual}}$ 
where i indicates the visit. The intercept, slope and SD residuals are the ones corresponding to the age at visit i. The intercept, slope and SD residuals are based on reference data.⁵⁸

Change in left ventricle posterior wall end diastole (LVPWed) SDS	From baseline (week 0) to visit 7 (week 26).	Score ^b	
Derived as the LVPWed SDS value at baseline week 0 subtracted from LVPWed SDS value at week 26 (visit 7) for Turner syndrome.
 
LVPWed SDS is derived as:
 $\text{LVPWed SDS}_i = \frac{\ln(\text{LVPWed})_i - \text{intercept} + \ln(\text{Weight}_i * \text{slope})}{\text{SD residual}}$ 
where i indicates the visit. The intercept, slope and SD residuals are the ones corresponding to the age at visit i. The intercept, slope and SD residuals are based on reference data.⁵⁸

Change in left ventricle inner dimension end diastole (LVIDed) SDS	From baseline (week 0) to visit 7 (week 26).	Score ^b	
Derived as the LVIDed SDS value at baseline week 0 subtracted from LVIDed SDS value at week 26 (visit 7) for Turner syndrome.
 
LVIDed SDS is derived as:
 $\text{LVIDed SDS}_i = \frac{\ln(\text{LVIDed})_i - \text{intercept} + \ln(\text{Weight}_i * \text{slope})}{\text{SD residual}}$ 
where i indicates the visit. The intercept, slope and SD residuals are the ones corresponding to the age at visit i. The intercept, slope and SD residuals are based on reference data.⁵⁸

Change in left ventricle inner dimension end systole (LVIDes) SDS	From baseline (week 0) to visit 7 (week 26).	Score ^b	
Derived as the LVIDes SDS value at baseline week 0 subtracted from LVIDes SDS value at week 26 (visit 7) for Turner syndrome.
 
LVIDes SDS is derived as:
 $\text{LVIDes SDS}_i = \frac{\ln(\text{LVIDes})_i - \text{intercept} + \ln(\text{Weight}_i * \text{slope})}{\text{SD residual}}$ 
where i indicates the visit. The intercept, slope and SD residuals are the ones corresponding to the age at visit i. The intercept, slope and SD residuals are based on reference data.⁵⁸

Title	Time frame	Unit	Details
Change in sitting height/height (SH/H)	From baseline (week 0) to visit 7 (week 26).	Ratio	Derived as SH/H at baseline week 0 subtracted from SH/H at week 26 (visit 7) for TS & ISS .
Change in sitting height/height SDS (SH/H SDS)	From baseline (week 0) to visit 7 (week 26).	Ratio	Derived as SH/H SDS at baseline week 0 subtracted from SH/H SDS at week 26 (visit 7) for TS & ISS . SH/H SDS is derived as: $\text{SH/H SDS}_i = \frac{\left(\frac{\text{SH}/H_i}{\text{population median}} \right)^{\text{Skewness}} - 1}{\text{Skewness} * \text{population SD}}$ where i indicates the visit. The population median and standard deviation are the ones corresponding to the age at visit i.
Change in bone age	From screening (visit 1) to visit 9 (week 52).	Ratio	The bone age/chronological age value at screening (visit 1) subtracted from the bone age value at week 52 (visit 9).

^aNegative score indicates that treatment burden is less compared to baseline.

^bPositive score indicates that the value is closer to or above the reference population compared to baseline.

^cNegative values indicate that the values are lower than the reference population.

^dNegative values indicate that the NAH is below the genetic height potential.

^eOnly to be collected from participants switching to somapacitan from daily GH treatment.

Height Velocity at visit 9 (week 52), Change in Height SDS from baseline (week 0) to visit 9 (week 52), Change in Height Velocity SDS from baseline (week 0) to visit 9 (week 52), Change in IGF-1 SDS from baseline (week 0) to visit 9 (week 52) and Change in IGFBP-3 SDS from baseline (week 0) to visit 9 (week 52) will be derived as parameters in the same way as the corresponding secondary endpoints at visit 7 (week 26).

The parameters will be summarised for relevant indications, SGA, TS, NS or ISS.

Pharmacokinetic and/or pharmacodynamic modelling

Pharmacokinetic (PK) and pharmacodynamic (PD) modelling based on the somapacitan concentration and IGF-I data from the study will be performed.

The objective of the PK/PD modelling analysis is to characterise the weekly PK/PD profile, weekly average exposure (C_{avg}) and weekly IGF-I average levels following somapacitan treatment in SGA, TS, NS and ISS.

A more technical and detailed elaboration of the PK/PD modelling will be given in a modelling analysis plan (MAP), which will be prepared prior to database lock.

Weekly average exposure (C_{avg}) based on population PK/PD modelling will be reported as a secondary endpoint. Other PK/PD modelling results will be reported in a separate modelling report,

which will not be part of the CSR. The individual somapacitan concentration data will be tabulated in the bioanalytical report.

